3.1 Inclusion-Criteria

Documented HIV-infection with current Hepatitis B infection, who are serological positive for HBSAg

Both, HIV- and HBV Infection must be confirmed by HIV ELISA and HBV HBsAg-testing (2 measurements of positive HBsAg > 6month interval). The viral load results will be included into the analyses, but are not part of the inclusion criteria.

As patients are enrolled retrospectively, data on liver enzymes (transaminases, gamma GT, AP, bilirubin) and viral load will be available, though this is not compulsory. Written informed consent will be provided prior to inclusion, or, if adequate, used from pre-existing cohort studies.

3.2. Exclusion-Criteria

PLWH with a cleared HBV-infection will be considered as HIV-monoinfected persons. Individuals younger than 18 years of age will be excluded from the analysis.

Patients with any social condition or living circumstances which may interfere with the conduct of the study, as anticipated by the investigator, such as incapacity to adequately understand the study content or not willing to cooperate will be excluded from the study.

For France, patients without adequate social security will be excluded.

4. Study Procedures

All participating PLWH will be recruited from the already existing national cohorts and defined networks of specialized HIV-clinics, respectively. This database will allow for the initial analysis of whether HDV screening was performed and allow to determine the HDV prevalence in the participating countries as well as study risk factors for HDV transmission.

Only patients who were alive in 2022 will be included into the study.

5. Plan of Analysis

Because of the observational nature of the study no predefined statistical power calculations can be made. Descriptive statistics will be used.

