1.1 Background

Hepatitis D is caused by a defective RNA-virus, that is known to be among the smallest human pathogenic viruses. As it partly shares the viral entry into hepatocytes with HBV, a coinfection is mandatory (1). Besides a simultaneous infection with HBV and HDV, it might also occur in the sense of a superinfection to a preexisting HBV-infection (2). Though most of the acute infections recover spontaneously, a progression to chronic disease is well described (3). The persistence of HDV leads to an accelerated fibrosis progression and eventually to cirrhosis and an increased risk of developing hepatocellular carcinoma (HCC) as well (4, 5). With the widely established feasibility of immunization against viral Hepatitis B, numbers of HDV-infection in high-income countries are quite low. Nevertheless, the burden of chronic HDV-infection worldwide is high, as different studies estimate the number of patients from 12 million to up to 72 million (6-8).

In the subgroup of people living with HIV (PLWH), who are at increased risk for acquiring viral hepatitis in general, rates of HDV infection have been reported between 10%-20% of HIV/HBV-coinfected people, with variations according to region as well as transmission group. Particularly, early in the HV epidemic higher rates of HDV have been reported for HIV/HBV coinfected drug users. More recently, a shift from people who acquired HIV through drug injection (PWID) to men who have sex with men (MSM) has been reported with HDV coinfection rates of around 8% (9). Common for all PLWH with HBV/HDV-coinfection is a more rapid progression in liver disease (10), resulting in increased rates of decompensated cirrhosis and higher mortality (11, 12). Therefore, mandatory screening for HDV was implemented into current EACS guideline recommendations. However, there is still a lack of testing in daily routine, even at sites where testing is easily accessible and reimbursed. Moreover, most PLWH

who are coinfecte with HBV are tested at initial HBV diagnosis, but after being put on antiretroviral treatment, which usually includes a tenofovir-based therapy a follow-up testing of HDV does not take place routinely.

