1.2 Objective

The aim of this project is to set up a cross-sectional cohort study (France, Germany, The Netherlands, Poland, Spain, Switzerland, Italy, United Kingdom and Portugal) to assess the implementation of EACS guidelines for HDV-testing among PLWH with positive HbsAg and thereby evaluate the prevalence of HDV infection among HIV/HBV-coinfected in 2023, as well as corresponding risk factors. In addition to the testing itself, this study will also set up a cohort and database for future HDV studies among PLWH, including clinical, virological und laboratory parameters.

1. Analyze the rate of HDV-testing and evaluate the prevalence of HDV-infection by testing.
 - a. Evaluation of former screening of HDV by assessing existing data at study sites.
 - b. Determination of the HDV prevalence in European PLWH and HBV coinfection.
2. Setting up a database of all PLWH with HBV/HDV coinfection
 - a. Analysis of transmission risk factors for HDV coinfection
 - b. Asses the rate of HDV positive patients with ongoing HDV replication.
 - c. Define the liver disease state by APRI score, fibroscan, ultrasound and routine laboratory test results.

2.Cohort Design and Methods

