7.1 Ethics

This retrospective multi-national cohort analysis has been submitted for ethical review to the ethics committee at Bonn University.

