7.4. Data Management

Data security will be assured for all patients participating in the study. All data management will be performed according to GCP. Data analysis will be performed by [name] (cooperating scientist; Amsterdam University Medical Centers) conducting to GCP.

8. Milestones

The patients being recruited are already tied to the different center sites and preexisting data are available. After writing consent, a retrospective analysis of these data can take place. Recruitment of patients is planned to run from November 2023 until April 2024.

MS	Title	Work pkg. (nr.)	Institution	Date (dd.mm.yyyy)	Proof of achievement/fulfillment
1	Study protocol for multicentric approach	1	University Hospital Bonn	15.11.2023	Study protocol
2	Ethics approval	1	University Hospital Bonn	30.11.2023	Ethics approval achieved
3	Agreement with cooperating centers	1	University Hospital Bonn	XX.XX.2023	Signed agreement
4	Start of patient enrolment	2 and 3	University hospital Bonn cooperating centers	XX.XX.2023	Electronic database established
5	Reaching 50% of respective HBs-Ag positive patients	2 and 3	University Hospital Bonn and cooperating centers	XX.XX.2024	50% of eligible/reachable patient population enrolled
6	Finishing patient acquisition	2 and 3	University Hospital Bonn and cooperating centers	XX.XX.2024	100% of patient population enrolled
9	Data Analysis	4	University Hospital Bonn and cooperating centers. Final data analyses by University Medical Centers Amsterdam	XX.XX.2024	Data analyses completed, and preparation of manuscript

9. Data Protection

All patient data that are used, have already been collected and country related databases have been set up. The included data are to be within the treating physicians keeping. The values that are evaluated in this study are shared with the other participating physicians, though data containing personal information are excluded from this. Collected data will be analyzed, evaluated and presented in an anonymous form, ensuring confidentiality of patient data towards third parties.

10. Literature:

2. Rizzetto M. Hepatitis D: thirty years after. *J Hepatol.* 2009;50(5):1043-50.

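### The open-ended social-circumstances exclusion in section 3.2 works against the representativeness aim and may under-represent patients at higher risk of HDV

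*Protocol*

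**What the plan says.** Protocol section 3.2 excludes "Patients with any social condition or living circumstances which may interfere with the conduct of the study, as anticipated by the investigator", and continues "such as incapacity to adequately understand the study content or not willing to cooperate will be excluded from the study". It then adds a country rule: "For France, patients without adequate social security will be excluded".

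The surrounding text describes a study built mostly on existing information. Section 7.1 says "This retrospective multi-national cohort analysis has been submitted for ethical review", and section 9 (Data Protection) says "All patient data that are used, have already been collected and country related databases have been set up". Section 3.1 describes enrolment as retrospective and lets consent from an earlier cohort study stand where it is adequate; otherwise written consent is needed before inclusion, as section 7.3 also requires. Section 4 recruits from existing national cohorts and networks of HIV clinics.

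The text is not uniform. Section 1.2 lists as its first aim "Analyze the rate of HDV-testing and evaluate the prevalence of HDV-infection by testing", and section 5.2 has HDV replication measured by PCR.

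Section 2.2 states an aim of representative data, with at least 20% of coinfected patients in each country. Section 5.1 defines prevalence over everyone with HIV and HBV in the database. Section 1.2 also lists "Analysis of transmission risk factors for HDV coinfection". On who carries the infection, section 1.1 says that "higher rates of HDV have been reported for HIV/HBV coinfected drug users", places this early in the epidemic, and then reports a more recent shift towards men who have sex with men (MSM), at around 8%.

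**The concern.** The exclusion rests on what an investigator anticipates and has no operational criteria. Because the two grounds are introduced as examples, they do not limit it. Such wording is usual where patients must attend visits and follow a treatment schedule. Here no visit or treatment schedule is described, and where an existing cohort consent is used, the patient need neither consent anew nor cooperate. An investigator may still remove that patient on social grounds.

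Two things are at stake. First, someone excluded under section 3.2 never enters the section 5.1 denominator, so no later analysis can recover them, and the protocol does not ask for excluded patients to be counted or described. If they carry HDV more often than the rest, the prevalence estimate is too low, and a larger sample does not cure it. Second, with nine countries and many sites each using their own judgement, part of any difference between countries could reflect how the clause was applied.

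**Working it through.** **Inputs from the protocol.** HDV prevalence in HIV/HBV coinfection of 10% to 20% (section 1.1), with 20% used for planning (section 2.2); about 8% in the more recent MSM group (section 1.1); n = 8000 coinfected persons (section 2.3).

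**The plan's own figure.** The nine country counts in section 2.2 sum to 800,000 if the Spanish entry is read as 150,000. Then 800,000 × 0.05 = 40,000 and 40,000 × 0.20 = 8,000, so the figure reproduces. It serves here only as the sample size.

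**Inputs not in the protocol (assumptions).** The share of patients excluded, f, and the ratio R of HDV prevalence in the excluded to the average prevalence p. I take f from 2% to 10% and R from 1 to 3.

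**Effect on prevalence.** The observed prevalence is (p − f·R·p)/(1 − f).

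- p = 20%, f = 5%, R = 2: (0.20 − 0.05 × 0.40)/0.95 = 0.18/0.95 = 18.9%, a bias of −1.05 points.
- p = 10%, f = 5%, R = 2: (0.10 − 0.05 × 0.20)/0.95 = 0.09/0.95 = 9.5%, a bias of −0.53 points.

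Bias in percentage points over the range:

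| f | R | p = 20% | p = 10% |
|---|---|---|---|
| any | 1 | 0 | 0 |
| 2% | 2 | −0.41 | −0.20 |
| 2% | 3 | −0.82 | −0.41 |
| 5% | 2 | −1.05 | −0.53 |
| 5% | 3 | −2.11 | −1.05 |
| 10% | 2 | −2.22 | −1.11 |
| 10% | 3 | −4.44 | −2.22 |

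**Sampling error for scale.** The 95% half-width is 1.96 × √(p(1 − p)/8000).

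- p = 20%: 1.96 × √(0.16/8000) = 0.88 points.
- p = 10%: 1.96 × √(0.09/8000) = 0.66 points.

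In the central illustration (f = 5%, R = 2) the bias exceeds the half-width at 20% (1.05 against 0.88) but not at 10% (0.53 against 0.66). With 2% excluded it stays below the half-width throughout the table.

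**Effect on the drug-use association.** Assume 20% prevalence in drug users and apply the 8% figure to everyone else, so the true ratio is 0.20/0.08 = 2.50.

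- 30% of drug users excluded regardless of HDV status: 0.20 × 0.7/(0.20 × 0.7 + 0.80 × 0.7) = 20%, so the ratio stays at 2.50. Drug users become a smaller share of the cohort and their estimate less precise.
- 40% of HDV-positive and 20% of HDV-negative drug users excluded: 0.12/(0.12 + 0.64) = 15.8%, ratio 1.97.
- 20% and 30% excluded: 0.16/(0.16 + 0.56) = 22.2%, ratio 2.78.

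The ratio therefore moves only if exclusion also depends on HDV status, and it can then move either way.

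**The case against.** The strongest defence is that the clause's own examples concern capacity and cooperation, which are proper grounds wherever new written consent is sought. Patients lost on those grounds would be lost under any lawful wording, so only exclusions beyond them can be charged to the clause. This stands, and it makes the attributable bias smaller than the total effect of all exclusions.

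A reader might infer that the study uses records only and that the clause has no function at all. The documents do not support that: sections 1.2 and 5.2 speak of testing and PCR, and sections 3.1 and 7.3 require consent. Mainly retrospective is as far as the text goes.

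A reader might also infer that people who inject drugs are the group excluded and that the drug-use association is therefore weakened. Section 3.2 does not mention drug use, and section 1.1 ties the higher rates to an earlier period before reporting the shift to MSM. That drug users would be over-represented among those excluded is plausible but remains an inference. Even if it is true, selection on drug use alone leaves the prevalence ratio unchanged.

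Large biases can be produced, but only from undocumented inputs. A fall from 20% to 14.9% needs drug users to be 25% of the cohort, half of them excluded, and 8% prevalence in everyone else. That implies (0.20 − 0.75 × 0.08)/0.25 = 56% prevalence in drug users, and then (0.125 × 0.56 + 0.75 × 0.08)/0.875 = 14.9%. The protocol gives neither the 25%, the exclusion rate nor the 56%.

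None of this answers the remaining difficulty: the examples do not bound the clause, and it has no clear purpose where existing consent and existing records are used.

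**Conclusion.** The concern holds in a limited form. An investigator-judged social exclusion without criteria conflicts with the aim of representative data in section 2.2, can be applied unevenly, and may under-represent marginalised patients. Downward bias in prevalence is conditional on the excluded having more HDV than the rest; with equal prevalence there is none. The description of risk populations is distorted if exclusion differs between risk groups, but bias in the drug-use ratio is not established.

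The size is unknown. Under the assumed range of 2% to 10% excluded at one to three times the average prevalence, the bias runs from 0 to −4.4 points at 20% and from 0 to −2.2 points at 10%. It can therefore exceed sampling error at n = 8000 but need not. The case for acting is that the loss cannot be repaired at analysis and the change is small.

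**What to change.** Replace the social-circumstances sentence in section 3.2 with: *Patients who refuse consent, or who lack capacity to consent where new consent is required, will be excluded.* Add that this does not apply to patients whose existing records are used under an adequate pre-existing cohort consent. The right to withdraw in section 6 is unaffected, and the French social-security rule stays as it is.

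Report aggregate counts of exclusions by reason and country, including those under the French rule. Break them down by transmission group only where the existing cohort's data permissions allow it, because recording that item for people who refused or could not consent would itself need a legal basis.

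The cost is a short protocol edit and a simple tally at each site. The small downside is that some records with less complete data will enter the database.

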5.1 Epidemiology

- Prevalence of HDV among HBV-coinfected PLWH
- Description of populations at risk
- Transmission risk factors

Methods:

- Prevalence: Number of HDV-positive persons in relation to all HBV/HIV individuals of the database.
- Risk populations and transmission factors: Descriptive methods will be used to investigate populations at risk and transmission risk factors.

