2.1 General

In this multi-center cohort study patients with documented HIV/HBV-coinfection (2 measurements of positive HBsAg > 6month interval and Anti-HBc-positive) will be evaluated for past HDV screening (last 24 months).

Eligible participants must be 18 years of age or older.

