2.2 Study Centers and Accrual of Patients

To secure representative data, each cohort or clinic network will aim to enroll a sample size of at least 20% of all HIV/HBV-coinfected individuals in each country. France, Switzerland, Italy, and The Netherlands already have well established national cohorts which are representing more than 50% of all PLWH in their respective countries. In the remaining countries (Germany, Spain, Poland, Portugal, UK) well-defined cohorts in specialized HIV-clinics or networks of HIV-centers are existing, which allow for a sufficient recruitment. The overall number of participants is planned to reach at least 8000 HIV/HBV-coinfected persons. With an estimated 800.000 PLWH in the following 9 countries: Spain 150.00, France 190.000, Germany 93.000, England 106.000, Portugal 61.000, Italy 140.000, Poland 20.000, Switzerland 16.000, Netherlands 24.000, and an estimated HBV-Prevalence of 5%, this would lead to a cohort of around 40.000 HIV/HBV coinfecte individuals. According to current data, 20% of HIV/HBV-coinfected PLWH are expected to have an HDV-infection, which should add up to 8000 individuals that would be needed to be studied. This should guarantee a representative sample size and would represent a highly meaningful European cohort for future HDV studies.

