2.3 Accrual goal

A cohort of 8000 HIV/HBV-coinfected individuals with serological HDV-screening evidence.

3. Patient Inclusion and Exclusion Criteria

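### The Section 5.1 prevalence formula would count anyone without an HDV result as HDV-negative, and the protocol does not settle whether such persons are in the database

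*Protocol*

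**What the plan says.** Section 5.1 defines the estimate: "Prevalence: Number of HDV-positive persons in relation to all HBV/HIV individuals of the database". The denominator is not limited to persons with an HDV result.

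Section 3.1 sets the entry condition: "Documented HIV-infection with current Hepatitis B infection, who are serological positive for HBSAg", confirmed by two HBsAg measurements more than six months apart. HDV status plays no part in it. Section 2.1 adds a look-back for past HDV screening over 24 months. Section 4 says of the recruited cohorts: "This database will allow for the initial analysis of whether HDV screening was performed".

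Two places suggest that results may be complete. Section 2.3 sets the goal as "A cohort of 8000 HIV/HBV-coinfected individuals with serological HDV-screening evidence". The first aim in Section 1.2 is "Analyze the rate of HDV-testing and evaluate the prevalence of HDV-infection by testing", and the same section begins a sentence with "In addition to the testing itself, this study will also set up a cohort and database for future HDV studies among PLWH". Section 2.2 gives the same number without mentioning an HDV result: "The overall number of participants is planned to reach at least 8000 HIV/HBV-coinfected persons".

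**The concern.** HDV prevalence among people with HIV and HBV is a main aim of the study. A person with no HDV result cannot be counted as positive. If that person stays in the denominator, the formula treats them as negative, whatever their true status.

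The protocol gives reasons to expect such persons. Entry does not require a result. Section 1.1 says that HDV testing is lacking in everyday care and that follow-up testing is not routine once antiretroviral treatment has begun. Sections 7.1 and 9 describe a retrospective analysis of data already held. Section 5.2 covers PCR in persons with positive serology, but no section describes serology for those without a result.

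If they are included, cohort prevalence is understated whenever any of them is infected. Two countries with equal prevalence would differ on paper if they tested to different degrees, and risk groups compared on the same ratio would be distorted in the same way.

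**Working it through.** **Inputs from the protocol**
- Planned size: 8000 (Sections 2.2 and 2.3).
- Expected HDV prevalence: 20% (Section 2.2). Section 1.1 gives a reported range of 10% to 20%.
- Testing coverage c, the share of the database with an HDV result: not given. Every value below is an assumption.

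**The plan's own figure.** The nine country counts in Section 2.2 sum to 800,000 (reading the Spanish figure as 150,000). 800,000 × 0.05 = 40,000, and 40,000 × 0.20 = 8,000. The figure reproduces. It says nothing about how many persons will have an HDV result, so it does not inform c.

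**What the formula yields.** With p the prevalence among the tested, positives = N × c × p. Dividing by N gives c × p.

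| Assumed coverage | Reported if p = 20% | Reported if p = 10% |
|---|---|---|
| 100% | 20% | 10% |
| 95% | 19% | 9.5% |
| 90% | 18% | 9% |
| 80% | 16% | 8% |
| 70% | 14% | 7% |

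Two countries with the same 20% and assumed coverages of 90% and 70% would report 18% and 14%.

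**Against sampling error.** The 95% half-width with all 8000 tested is 1.96 × √(p(1−p)/8000): 0.88 points at 20% and 0.66 at 10%. If testing is unrelated to infection, the bias is p(1−c). It equals the half-width at c = 1 − 0.0088/0.20 = 0.956, and at c = 1 − 0.0066/0.10 = 0.934. At 97% coverage and p = 20% the bias is 0.20 × 0.03 = 0.6 points, less than the half-width.

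**With no assumption about the untested.** Cohort prevalence lies between c × p and c × p + (1 − c). At p = 20% this is 18% to 28% for c = 90%, and 14% to 44% for c = 70%. Section 5.1 reports only the lower end.

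**Is a tested-only denominator better?** Not automatically. Suppose 20% of persons have prevalence 40% and 95% of them are tested, while the other 80% have prevalence 5% (all assumed). Truth: 0.20 × 0.40 + 0.80 × 0.05 = 12.0%.
- Low-risk group 80% tested: Section 5.1 gives 0.076 + 0.032 = 10.8%. Coverage is 0.19 + 0.64 = 83%. Tested-only gives 0.108/0.83 = 13.0%. The errors are −1.2 and +1.0 points.
- Low-risk group 50% tested: Section 5.1 gives 0.076 + 0.020 = 9.6%. Coverage is 0.19 + 0.40 = 59%. Tested-only gives 0.096/0.59 = 16.3%. The errors are −2.4 and +4.3 points.

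Tested-only prevalence therefore has to be read beside the coverage and the lower bound.

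**The case against.** The strongest reply is that everyone in the analysed database may have a result. Section 2.3 describes the 8000 as having screening evidence, and Section 1.2 speaks of prevalence by testing. Section 1.2 also lists the review of former screening separately from the determination of prevalence, and Section 4 calls the screening check an initial analysis. This fits a two-step design: audit past screening first, then test. The lack of testing in Section 1.1 would then describe the starting position and not the final denominator, and Section 5.1 would be unbiased.

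This reply stands as a possible reading. It is not established, because no testing step is written down, Section 2.3 is a target and not an entry criterion, and Sections 7.1 and 9 point to existing data.

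A reader might go further and infer that untested persons must be present, because a testing rate is an aim and would otherwise be 100%. The documents do not support that. The look-back in Section 2.1 is 24 months, so an older test can be screening evidence while the 24-month rate is below 100%. A reader might also take Sections 2.2 and 2.3 to contradict each other. Section 2.2 is merely silent about a result, and an accrual goal can be narrower than an eligibility rule.

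The objection that the coverage values are unsourced is correct. So is the point that a tested-only figure can err more than the Section 5.1 ratio when testing is selective; the remedy has to allow for that.

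**Conclusion.** The point holds in conditional form. Section 5.1 states a denominator that treats persons without an HDV result as negative, Section 3.1 lets them in, and no procedure is described that would give them a result. This is a stated rule, not detail left to an analysis plan. Whether such persons will be in the database is unresolved, because Sections 1.2 and 2.3 allow a reading in which there are none.

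It would go too far to conclude that the planned estimate is biased, or that a contradiction between sections is certain. If everyone has a result, the bias is zero. If not, the estimate is coverage times prevalence among the tested: at 20% among the tested, 18% at an assumed 90% coverage and 14% at 70%. The 20% is the protocol's expectation for all coinfected persons, used here for the tested as an assumption. The comparison with sampling error further assumes that testing is unrelated to infection.

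This should be fixed before analysis. With the size wholly dependent on an unstated coverage, it does not rank as an established error in the main result.

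**What to change.** - In Section 5.1, use persons with an HDV serology result as the denominator for prevalence and for risk-group comparisons. Nothing changes if everyone has one.
- Beside it, report the number and share with a result, overall and by country. Give the all-database ratio only as a lower bound for the cohort.
- State that tested-only prevalence may be too high if testing was aimed at higher-risk persons. Standardisation by country and transmission group is an optional sensitivity analysis for the SAP. It would assume that testing is unrelated to infection within those strata.
- Reconcile Sections 2.3, 3.1, 4 and 5.1 on whether persons without a result are in the database.

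**Cost.** A few sentences and a slightly wider interval. With 8000 in the database, 20% among the tested and 90% coverage, the half-width goes from 1.96 × √(0.18 × 0.82/8000) = 0.84 points to 1.96 × √(0.20 × 0.80/7200) = 0.92. At 80% coverage it goes from 0.80 to 0.98. The change itself requires no extra enrolment. If Section 2.3 means 8000 persons with a result, that figure can be restated as the number actually available.

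### Section 5.1 gives only descriptive methods for transmission risk factors; comparisons should also be stratified by country, among persons with an HDV result

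*Protocol*

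**What the plan says.** Objective 2a in section 1.2 is the "Analysis of transmission risk factors for HDV coinfection". Section 5 sets the general method: "Descriptive statistics will be used". Section 5.1 repeats this for the objective: "Descriptive methods will be used to investigate populations at risk and transmission risk factors". Neither section mentions country.

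Section 1.1 gives HDV rates of 10% to 20% among HIV/HBV-coinfected people, "with variations according to region as well as transmission group".

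For prevalence, section 5.1 defines one proportion: "Number of HDV-positive persons in relation to all HBV/HIV individuals of the database". Two other places differ from it. Section 4 expects the database to "determine the HDV prevalence in the participating countries as well as study risk factors for HDV transmission". Section 2.3 sets the accrual goal as "A cohort of 8000 HIV/HBV-coinfected individuals with serological HDV-screening evidence".

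**The concern.** Section 1.1 names region as a source of variation in HDV, alongside the exposure that objective 2a is to study. Country therefore meets one of the two conditions for a confounder on the protocol's own account. The other condition is that the transmission mix differs between countries; the protocol gives no figures on this. If it does differ, an apparent risk factor may only mark a country with much HDV, or a real one may be hidden. The method in 5.1 does not guard against this, although the design already records country.

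The denominator matters for the same comparisons. If the database holds persons with no HDV result and they stay in the denominator, they count as non-cases. That lowers prevalence, and it distorts comparisons between groups if testing differs between them.

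**Working it through.** **The plan's own figure.** The nine country counts in section 2.2 (reading Spain's as 150,000) sum to 800,000 PLWH. 800,000 × 5% HBV × 20% = 8000, which reproduces the target. It serves below as the illustrative sample size.

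**Confounding by country (illustration only).** Assumed: two country strata, A and B, of 4000 persons each, all with an HDV result, and no effect of exposure within either stratum. HDV prevalence pA and pB is taken within the 10% to 20% of section 1.1. The exposed shares a and b are invented, because the protocol gives none.

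Crude prevalence in the exposed = (a·pA + b·pB)/(a + b). In the unexposed it is the same expression with 1−a and 1−b.

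For pA = 10%, pB = 20%, a = 10%, b = 40%:
- Exposed: 400 + 1600 = 2000 persons, 40 + 320 = 360 positive, 18%.
- Unexposed: 3600 + 2400 = 6000 persons, 360 + 480 = 840 positive, 14%.
- Crude ratio 18/14 = 1.29. Log standard error √(1/360 − 1/2000 + 1/840 − 1/6000) = 0.0574; 95% interval 1.15 to 1.44.
- Mantel-Haenszel numerator 40·3600/4000 + 320·2400/4000 = 228; denominator 360·400/4000 + 480·1600/4000 = 228. Ratio 1.00, interval 0.89 to 1.12.

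| HDV in A / B | Exposed share in A / B | Exposed v unexposed, crude | Crude ratio (95% interval) |
|---|---|---|---|
| 10% / 20% | 10% / 40% | 18% v 14% | 1.29 (1.15–1.44) |
| 10% / 20% | 20% / 30% | 16.0% v 14.7% | 1.09 (0.97–1.23) |
| 10% / 20% | 30% / 30% | 15% v 15% | 1.00 |
| 10% / 20% | 40% / 10% | 12% v 16% | 0.75 (0.66–0.86) |
| 10% / 15% | 10% / 40% | 14% v 12% | 1.17 (1.03–1.33) |
| 10% / 15% | 20% / 30% | 13.0% v 12.3% | 1.05 (0.92–1.20) |

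The stratified ratio is 1.00 in every row, because there is no effect within strata. A marked imbalance produces a spurious association in either direction; a modest one stays within chance; an equal mix gives none.

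**Precision cost of stratifying.** The half-width on the log scale goes from 0.113 to 0.117 for shares 10%/40%, and from 0.132 to 0.140 for 40%/10%. It does not widen with equal shares.

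**Denominator.** Let t be the proportion of persons with a result, and suppose that those tested are like those not tested. Counting the untested as non-cases turns a prevalence P into t·P. It turns a ratio R between groups 1 and 0 into R·t1/t0. If everyone in the database has a result, t = 1 and the two denominators coincide.

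**Precision by country.** At 20% enrolment, n = PLWH × 0.05 × 0.20. Switzerland has 160 persons: half-width 1.96·√(0.09/160) = 4.6 points at 10% HDV and 1.96·√(0.16/160) = 6.2 points at 20%. France has 1900: 1.3 and 1.8 points.

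**The case against.** The strongest reply is that nothing here is a stated error. No section says that transmission groups will be compared pooled over countries. Tables by country are themselves descriptive, and adjustment variables are often left to a statistical analysis plan, which was not available here. Crude prevalence by transmission group is also a legitimate quantity for describing who carries HDV, and the protocol promises no adjusted or causal effect. All of this stands. It is why the tables should stay and why the point is an improvement to the stated method.

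The illustration is also open to attack. The 10% to 20% in section 1.1 is a range of reported rates that vary by region and by transmission group. It is not a range between these nine countries, yet the illustration assigns the variation wholly to country. That stands too: the figures show a mechanism and do not estimate a bias.

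A reader might go further and infer that the overall prevalence is biased by unequal enrolment and must be weighted. The protocol does not support this. Section 2.2 aims for "at least 20% of all HIV/HBV-coinfected individuals in each country". France, Switzerland, Italy and the Netherlands hold (190 + 16 + 140 + 24)/800 = 46.25% of PLWH. With 20% enrolled everywhere they form 46.25% of the sample too, so the shift is zero. A shift needs unequal enrolment: assuming 50% in these four and 20% in the other five, their sample share is 185/(185 + 86) = 68.27%, and a 10-point HDV difference between the two sets moves the overall figure by 2.2 points. But section 2.2 says only that these cohorts represent more than half of PLWH in their countries, not that half will be enrolled. The weights would also rest on a uniform 5% HBV prevalence. Section 4 already foresees prevalence in the participating countries.

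**Conclusion.** The point holds as a free improvement. The only method stated for objective 2a leaves risk-factor comparisons unprotected against country, although section 1.1 names region as a source of variation. Whether there would be confounding depends on differences in transmission mix that the protocol does not give. The crude ratios of 0.75 to 1.29 rest wholly on assumed strata, prevalences and shares.

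The prevalence method in 5.1 should also be brought into line with section 4 on country and with section 2.3 on persons with screening evidence. The denominator matters only if the database holds persons without an HDV result.

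Two stronger readings are not supported: that the protocol plans pooled comparisons, and that the overall prevalence needs weighting.

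**What to change.** In section 5.1:
- Keep the descriptive tables. Add a comparison of transmission groups stratified by or adjusted for country, for example a Mantel-Haenszel ratio, among HIV/HBV persons with an HDV result, positive or negative.
- Label any unstratified comparison as crude.
- Report prevalence by country with intervals, as section 4 foresees, on the denominator of persons with an HDV result, in keeping with section 2.3.
- Add no weighted overall prevalence.

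No new patients or procedures are needed. The cost is slightly more analysis, a marginally wider interval for the stratified ratio, and country figures that will be imprecise in small countries such as Switzerland.
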